### **4.4.2. Completers Population (CP)**

This CP population consists of all patients in the MITT population who completed the extension study based on the study completion status collected on the End of Study CRF page. No missing data will be imputed for this analysis. Any substantial differences between conclusions based on the MITT population and the CP population will be investigated. Note that CP population will be used only for endpoints that include the endoscopy subscore, unless otherwise stated.

### **4.4.3. Safety Population**

The Safety population will include all patients who received study medication in the extension study.

## **5. PATIENT DISPOSITION**

### **5.1. Disposition**

The number of patients enrolled in the study will be tabulated overall and by country as described in Section 4. Tables will indicate the number and percentage of patients who were enrolled into the study, who completed treatment and/or completed the study and who discontinued treatment and/or discontinued study prematurely (early termination) for any of the following reasons:

- Adverse event(s) (AEs)
- Patient lost to follow up
- Patient withdrawal of consent
- Investigator decision
- Sponsor decision
- Death
- Other

All percentages will be based on the number of enrolled patients within the relevant category.

Patient disposition data will be presented in a listing.

## 5.2. Protocol Deviations

Protocol deviations will be summarized for the Safety population and will include the number of patients with at least one protocol deviation, total number of protocol deviations and summaries by subtype category.

Protocol deviations will be presented in a listing.

## 6. DEMOGRAPHICS AND BASELINE CHARACTERISTICS

Since this is an extension study to APD334-003 study, some of the baseline characteristics data (i.e. ulcerative colitis history, social history and medical history) for the relevant enrolled patients will be taken from the APD334-003 induction study.

### 6.1. Demographics

All baseline patient characteristics of demographics data will be presented for the Safety population. Demographic characteristics will be collected at Week 12 (APD334-003 study) / Day -1 (APD334-005 study).

The demographic characteristics consist of age (years), sex, race, and ethnicity. A patient's age in years is calculated using the date of the informed consent and date of birth.

The baseline characteristics consist of baseline height (cm), baseline weight (kg), and baseline body mass index (BMI) (kg/m^2). Body mass index is calculated as (body weight in kilograms) / (height in meters).

Continuous variables (i.e. age, height, weight and BMI) will be summarized using descriptive statistics (i.e. number of observations [n], mean, SD, median, minimum and maximum). Categorical data will be summarized by the number and percentage (n(%)) of patients within the relevant category i.e. age category (18-24; 25-34; 35-44; 45-54; 55-65; and >65), sex (Male, Female), race (American Indian or Alaska Native, Asian – Chinese, Asian – Japanese, Asian – Other, Black or African American, Native Hawaiian or Other Pacific Islander, White, Other and Not allowed per country regulation) and ethnicity (Hispanic or Latino, Not Hispanic or Latino). Percentages will be based on the total number of patients in the Safety population.

Patient demographics and baseline characteristics will be presented in a listing. In addition patient weight data will be listed.

### 6.2. Baseline Disease Characteristics

Baseline ulcerative colitis disease information will be summarized for the Safety population as follows:

- Duration of ulcerative colitis (years) at APD334-003 screening visit by descriptive statistics
- Disease location (Proctosigmoiditis/Left sided colitis, Pancolitis/ Extensive colitis) at APD334-003 screening visit by n (%)
- History of Colonic Ulcerative Activity on Endoscopy (ulcerative colitis extending  $\geq$  15 cm proximal to the rectum) at APD334-003 screening visit by n (%)

- Ulcerative colitis prior

[REDACTED]

Note: Prior ulcerative colitis treatment was collected at APD334-003 screening visit.

- Disease Activity (Mayo Clinic Scores) at APD334-005 baseline
- Fecal Calprotectin at APD334-005 baseline
- CRP at APD334-005 baseline

[REDACTED]

Baseline ulcerative colitis disease information collected at APD334-003 screening visit, including hospitalization history, will be listed.

### **6.3. Alcohol, Tobacco and Caffeine Usage**

Social history collected at APD334-003 screening visit i.e. tobacco, alcohol, caffeine and other substances used, will be listed for the Safety population.

### **6.4. Medical History**

Medical history will be coded using the Medical Dictionary for Regulatory Activities (MedDRA) Version 18.0 or later. The number and percentage of patients with any medical history at APD334-003 screening visit will be summarized overall and for each system organ class and preferred term. Percentages will be calculated based on number of patients in the Safety population.

Patient medical history data including specific details will be presented in a listing.

### **6.5. Inclusion and Exclusion Criteria**

Inclusion and exclusion data will be listed only for patients that did not meet inclusion/exclusion criteria.

## 7. TREATMENTS AND MEDICATIONS

### 7.1. Concomitant Medications

Concomitant medications include any medications that are taken when on study treatment in APD334-005 study, including medications that started prior and are ongoing during study treatment.

The total number of concomitant medications and the number and percentages of patients with at least one concomitant medication will be summarized as described in Section 4. The number and percentages of all concomitant medications will be summarized by drug class and preferred term. All summaries will be performed using the Safety population.

Medications will be coded using the World Health Organization Drug Dictionary (WHODRUG, Version December 2017).

All medications will be listed.

### 7.2. Study Treatments

Investigational product will be dispensed to eligible patients under the supervision of the investigator or his/her designee at the Week 12 visit of the APD334-003 study.

Patients enrolled under Protocol Amendment 02 (28 Sep 2015) were randomized to Placebo or 2 mg q.d. etrasimod and were instructed to take their 2 mg etrasimod, or matching Placebo tablet in the same way as described in the paragraph above.

Study treatment administration, drug accountability and dosing details will be listed for the Safety population.

#### 7.2.1. Treatment Compliance

Compliance will be assessed using patient data recorded in the drug accountability form of the electronic case report forms (eCRFs). On each day, a patient should take his/her assigned treatment.

The overall study drug compliance (%) will be calculated as follows:

Compliance (%) = [(actual number of tablets taken over the study period) / (designated total number of tablets that should have been taken over the study period)] \* 100

The study period is defined as the number of days that the patient has been in the active treatment phase of the APD334-005 study.

Summary statistics on percentage of treatment compliance as well as the number and percentage of patients in each compliance category (<80%, 80-100%, and >100% compliant) will be presented as described in Section 4 using the Safety population.

Treatment compliance data will be listed for each patient.

### **7.2.2. Extent of Exposure**

Duration of exposure is defined as the total number of days a patient is exposed to any study drug in APD334-005 study and will be presented as the sum of all days from the first dose date (Day 1) to the last dose date (i.e. date of last dose - the date of first dose + 1) using the dose administration page on the CRF. If the last dose date on the dose administration page is missing, or if a patient is lost to follow-up, but the drug accountability log confirms that the patient has taken study drug, the visit date following the last completed drug accountability log will be used.

The duration of exposure (in days and in weeks) to study drug will be summarized for all patients in the Safety population and will be presented in a table by summary statistics (as described in Section 4). The duration of exposure (cumulative) will then be classified into the following categories: > 0 days,  $\geq 28$  days,  $\geq 56$  days,  $\geq 84$  days,  $\geq 112$  days,  $\geq 140$  days,  $\geq 168$  days,  $\geq 196$  days,  $\geq 224$  days,  $\geq 252$  days and  $\geq 280$  days and will be presented as the number and percentage of patients in each duration category. Percentages will be computed from the number of patients in the Safety population.

In addition, the overall exposure will be summarized i.e. from Baseline of APD334-003 study to end of APD334-005 study. Duration of overall exposure is defined as the total number of days a patient is exposed to any study drug in APD334-003 and APD334-005 study and will be presented as the sum of all days from the first dose date (Day 1 of APD334-003 study) to the last dose date in the APD334-005 study (i.e. date of last dose - the date of first dose + 1) using the dose administration page on the CRF. If the last dose date on the dose administration page is missing, or if a patient is lost to follow-up, but the drug accountability log confirms that the patient has taken study drug, the visit date following the last completed drug accountability log will be used.

The duration of overall exposure (in days and in weeks) to study drug will be summarized for all patients in the Safety population and will be presented in a table by summary statistics (as described in Section 4). The duration of overall exposure (cumulative) will then be classified into the following categories: > 0 days,  $\geq 28$  days,  $\geq 56$  days,  $\geq 84$  days,  $\geq 112$  days,  $\geq 140$  days,  $\geq 168$  days,  $\geq 196$  days,  $\geq 224$  days,  $\geq 252$  days,  $\geq 280$  days,  $\geq 308$  days,  $\geq 336$  days and  $\geq 364$  days and will be presented as the number and percentage of patients in each duration category. Percentages will be computed from the number of patients in the Safety population.

A summary of each patient's exposure in APD334-005 study will be presented in a listing.

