## 4. GENERAL STATISTICAL CONSIDERATIONS

Continuous data will be summarized using descriptive statistics (i.e., n, mean, median, standard deviation (SD), 90% confidence interval (CI) for change or percent change from baseline, minimum and maximum). For the summary statistics of all numerical variables unless otherwise specified, minimum and maximum will be displayed to the same level of precision as reported. Mean, median and 90% CIs will be displayed to one level of precision greater than the data collected. Standard deviation will be displayed to two levels of precision greater than the data collected.

For proportion-based measures, n, frequencies, proportion and its 90% CI will be produced. The denominator for all percentages will be the number of patients within the treatment group for the analysis set of interest, unless otherwise stated. Percentages will be presented to 1 decimal place. When count data are presented, the percentage will be suppressed when the count is zero in order to draw attention to the non-zero counts. A row denoted “Missing” will be included in count tabulations where specified on the shells to account for dropouts and missing values.

There is no formal between group inferential comparisons for study endpoints due to lack of control group. Summary statistics will be provided for the primary safety endpoint, secondary efficacy endpoints, exploratory efficacy endpoints, and additional safety measures. All analysis summaries will be presented as follows:

Previously Treated in APD334-003 (APD334-005 treatment: 2 mg etrasimod)				APD334-005 treatment:	APD334-005 treatment:
Placebo	1 mg etrasimod	2 mg etrasimod	1 mg & 2 mg etrasimod	2 mg etrasimod	Placebo

[figure not shown]
[figure not shown]
Listings will include a subtitle to indicate both treatments, i.e. treatment received in APD334-003 study and treatment received in APD334-005 study.

[figure not shown]
[figure not shown]
[figure not shown]
If endoscopy was performed prior to Week 46, then last observation carried forward (LOCF) imputation method will be used for the endoscopy subscore. Any endoscopy performed during the APD334-005 extension study (after Week 12 visit) will be used for LOCF imputation.

All data summaries and statistical analyses will be performed using the SAS software version 9.3 or higher (SAS Institute, Cary, NC).

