## 12. CHANGES IN THE PLANNED ANALYSIS

Under Protocol Amendment 02 (28 Sep 2015) eligible responders on active treatment in the APD334-003 study (who choose to continue on to the APD334-005 study) underwent 1:1 randomization to 2 mg etrasimod q.d. or matching Placebo, while eligible Placebo responders in the APD334-003 study (who choose to continue on to the APD334-005 study) remained on Placebo. Responder patients stayed blinded. Non-responders in the APD334-003 study (who choose to continue on to the APD334-005 study) were administered with open-label 2 mg etrasimod. Under Protocol Amendment 03 (20 Oct 2016) eligible patients (who choose to continue on to the APD334-005 study) must have completed the APD334-003 study and were administered open-label 2 mg etrasimod. Data gathered on patients before Protocol Amendment 03 will follow the Protocol Amendment 03 analyses and data presentation as described in this SAP document. Patients that received 2mg etrasimod under any Protocol Amendment will be pooled into a 2 mg etrasimod group and patients that received placebo prior to Protocol Amendment 03 will be included in a second group. All listings will be presented by these two treatment groups, namely 2 mg etrasimod and Placebo, and by treatment previously received in APD334-003 study.

The following exploratory objectives have been added to the SAP in comparison with Protocol Amendment 04 (27 Mar 2017) to be consistent with the objectives in the APD334-003 study:

[REDACTED]

The following exploratory endpoints have been added to the SAP in comparison with Protocol Amendment 04 (27 Mar 2017) to be consistent with the endpoints in the APD334-003 study:

[REDACTED]

The following exploratory endpoints have been removed from the SAP in comparison with Protocol Amendment 04 (27 Mar 2017), as these are no longer needed:

[REDACTED]

The following subgroup analysis has been added to the SAP in comparison with Protocol Amendment 04 (27 Mar 2017):

[REDACTED]

The following subgroup analyses have been removed from the SAP in comparison with Protocol Amendment 04 (27 Mar 2017), as these have been already evaluated in APD334-003 study and are no longer needed:

[REDACTED]

The 95% CIs have been changed to 90% CIs for all analyses in comparison with Protocol Amendment 04 (27 Mar 2017) to be consistent with the APD334-003 study.

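### The SAP's overall exposure counts placebo days from APD334-003, so the pooled 2 mg column overstates time on etrasimod

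*SAP*

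**What the plan says.** SAP 7.2.2 defines two exposure durations. The first covers APD334-005 alone. The second, overall exposure, is the number of days "a patient is exposed to any study drug in APD334-003 and APD334-005 study", calculated as "the sum of all days from the first dose date (Day 1 of APD334-003 study) to the last dose date in the APD334-005 study", that is, last dose date minus first dose date plus 1. The definition does not mention placebo, but the formula counts every day in the span whatever was taken.

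For reporting, "The duration of overall exposure (in days and in weeks) to study drug will be summarized for all patients in the Safety population", with cumulative 28-day categories up to ≥364 days, in the layout of SAP Section 4. That layout has a block headed "Previously Treated in APD334-003 (APD334-005 treatment: 2 mg etrasimod"), split by APD334-003 treatment (placebo, 1 mg, 2 mg, and 1 mg and 2 mg combined). Two further columns follow, for 2 mg etrasimod and for placebo in APD334-005.

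SAP Section 12 explains who is in the pooled column: "Patients that received 2mg etrasimod under any Protocol Amendment will be pooled into a 2 mg etrasimod group". Under Amendment 02, "Non-responders in the APD334-003 study (who choose to continue on to the APD334-005 study) were administered with open-label 2 mg etrasimod", which includes placebo non-responders. From Amendment 03, eligible patients received open-label 2 mg whichever arm they had been in. Also under Amendment 02, responders on active treatment "underwent 1:1 randomization to 2 mg etrasimod q.d. or matching Placebo", and placebo responders stayed on placebo.

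**The concern.** The primary objective is the long-term safety and tolerability of etrasimod. In the readable text, overall exposure is the only summary of exposure duration that spans both studies, and the ≥308, ≥336 and ≥364 day categories appear only there. A reader who wants to know how long patients were on etrasimod will look at the pooled 2 mg column of that table. For patients who took placebo in APD334-003, about the first 12 weeks of the figure are placebo. The same holds in the prior-placebo column.

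**Working it through.** **Inputs**
- APD334-003 lasts 12 weeks (Protocol Synopsis, Study Design): 12 × 7 = 84 days.
- APD334-005 treatment lasts 34 weeks (Protocol Synopsis): 34 × 7 = 238 days.
- Under Amendment 02 the final assessment was at Week 52 (SAP 3.1): 52 × 7 = 364 days in total, of which (52 − 12) × 7 = 280 in APD334-005.
- s, the share of the pooled 2 mg column that took placebo in APD334-003, is not given. Assumed: 10%, 25% and one third (the last if the three APD334-003 groups enrolled equally).
- Dropout is not given. Where used, it is an assumption, spread evenly over days 1 to 237 of APD334-005.

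**The plan's own figure.** 12 + 34 = 46 weeks, or 46 × 7 = 322 days. This reproduces.

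**Per patient, full planned duration, 2 mg in APD334-005**

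| Sequence | Shown as overall exposure | On etrasimod | Difference |
|---|---|---|---|
| Placebo then 2 mg, 46 weeks | 322 | 238 | 84 |
| Active then 2 mg, 46 weeks | 322 | 322 | 0 |
| Placebo then 2 mg, 52 weeks (Amendment 02) | 364 | 280 | 84 |

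**Categories.** 84 = 3 × 28. The 46-week prior-placebo completer is counted at ≥252, ≥280 and ≥308 days, but the highest category reached on etrasimod is ≥224. The shift is three categories if the added span is exactly 84 days. It can differ by one otherwise: with 83 days, a patient stopping at day 28 is shown at 111 and moves two; with 85, a patient stopping at day 27 is shown at 112 and moves four.

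**Pooled mean.** Mean shown − mean etrasimod days = 84 × s, whatever the dropout in APD334-005.
- s = 10%: 8.4 days
- s = 25%: 21.0 days
- s = one third: 28.0 days

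If everyone completes 46 weeks, mean etrasimod days are 322 − 84s = 313.6, 301.0 and 294.0, against 322 shown.

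**Share at ≥308 days, 46-week schedule.** A prior-placebo patient has at most 238 etrasimod days, so the share on etrasimod is (1 − s) × the share shown.
- No dropout: 100% shown, against 90%, 75% and 67%.
- 20% dropout: to be shown at ≥308, a dropout must stop on days 224 to 237 (14 of 237 days). Shown: 0.80 + 0.20 × 14/237 = 81%. On etrasimod: 73%, 61% and 54%.

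**Pooled median.** With dropout d below 50%, the median shown is 322. The median of etrasimod days stays at 322 while (1 − s)(1 − d) is at least 0.5. At s = one third this fails once d exceeds 1 − 0.5/(2/3) = 25%; at s = 25%, once d exceeds 1 − 0.5/0.75 = 33%; at s = 10%, once d exceeds 1 − 0.5/0.90 = 44%. At d = 40% the etrasimod median is 322, 282 and 238 for s = 10%, 25% and one third.

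**The case against.** The strongest reply is that nothing is miscalculated. The SAP calls the quantity overall exposure to any study drug and never calls it etrasimod exposure. That stands.

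The layout also helps. The prior 1 mg, prior 2 mg and combined columns contain only patients on etrasimod throughout, and the prior-placebo column sits beside the pooled one. In the 2 mg columns, the APD334-005-only table measures time on 2 mg etrasimod correctly.

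A reader might infer that etrasimod time cannot be recovered, since SAP 7.2.2 lists only APD334-005 exposure ("exposure in APD334-005 study will be presented in a listing"). The documents do not support that. SAP Sections 4 and 12 present listings by APD334-003 treatment, and entrants had completed the 12-week study. Adding about 84 days for prior active treatment and none for prior placebo gives an approximate figure per patient; only exact values are missing.

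A reader might also infer that the APD334-005 placebo column misleads. It does mix patients with no etrasimod and patients with about 84 prior etrasimod days, but its heading hardly invites anyone to read it as time on etrasimod.

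Finally, the table shells are not in the documents, so a clarifying title or footnote may already exist. None of this makes the pooled 2 mg figure a measure of time on etrasimod.

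**Conclusion.** The point holds as a minor one about a descriptive table. In the pooled 2 mg column and the prior-placebo column, overall exposure exceeds time on etrasimod by about 84 days for each patient given placebo in APD334-003, which is about three duration categories. That figure rests only on completion of the 12-week study. The effect on the pooled column depends on s: 8.4 to 28 days on the mean for assumed s of 10% to one third. The median is unchanged with little dropout, but at s = one third it falls once assumed dropout exceeds 25%.

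It would be wrong to infer that the safety results are affected. The adverse-event percentages use patient counts in the Safety population, and no endpoint uses this duration. The remaining risk is that the pooled figure is read or cited as time on etrasimod.

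**What to change.** In SAP 7.2.2, add or substitute an overall etrasimod exposure: etrasimod days in APD334-003 (zero if placebo) plus etrasimod days in APD334-005 (zero if placebo). Use it for the overall summary statistics and the cumulative categories. Label it *any etrasimod dose (1 mg or 2 mg)* or split it by dose, because a prior-1 mg completer of the 46-week schedule has about 84 days on 1 mg and 238 on 2 mg. If the present span is kept, title it *time on any study treatment, including placebo*.

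The cost is one extra derivation from dosing dates and treatment codes, and smaller exposure figures in the pooled 2 mg column. Retitling alone needs no new derivation, but it does not supply the etrasimod figure.

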## **8. EFFICACY ANALYSIS**

Summary statistical analyses will be performed for all efficacy measures.

There is no between group inferential comparison for study endpoints.

### **8.1. Efficacy Assessments**

Efficacy assessments will be listed for each patient for the MITT population where relevant.

### 8.1.1. Flexible Proctosigmoidoscopy

A flexible proctosigmoidoscopy, performed with a video endoscope following a cleansing prep (oral or rectal cathartic) will be performed at Baseline [REDACTED] and [REDACTED] EOT. A repeat flexible proctosigmoidoscopy may be permitted by the Sponsor when the central reader indicates that the video endoscope data was acquired incorrectly, or did not meet the minimal required quality standards.

### 8.1.2. Stool Sample

A stool sample will be collected at time points listed in the schedule of procedures and visits (Section 14.1) for the analysis of fecal calprotectin, [REDACTED]

### 8.1.3. C-reactive protein (CRP)

Blood samples for analysis of CRP will be collected at time points listed in the schedule of procedures and visits (Section 14.1).

### 8.1.4. Electronic Clinical Outcomes Assessments (eCOA)

Patient reported outcomes (stool frequency and rectal bleeding) will be captured daily using a handheld electronic device from CRF Health [REDACTED]. Diary entries will be reviewed by site personnel during scheduled visits and at any unscheduled visit(s) due to disease exacerbation. The CRF Health eDiary software runs on the device and includes all the security features required of an eCOA solution for 21 CFR Part 11 compliance.

[figure not shown]
[REDACTED]

[figure not shown]
[REDACTED]

[REDACTED]

[REDACTED]

[REDACTED]

